All secondary outcomes assessed 14 months after baseline. In MyHC-T2D intervention arm, 14 months post baseline corresponds to approximately 12 months after the main component of the MyHC-T2D intervention.	
Hypoglycemia: % time glucose < 54 mg/dL, % time glucose < 70 mg/dL, # of events ≥ 15 minutes glucose 54-69 mg/dL, # events ≥ 15 minutes glucose < 54 mg/dL, # of events ≥ 15 minutes glucose < 70 mg/dL between 12 AM and 6AM
 
Hyperglycemia: % time glucose > 180 mg/dL, % time glucose > 250 mg/dL
 
Time in range: % time between 70 to 180 mg/dL
 
Glucose Management Indicator
 
Average glucose
 
Glucose variation: coefficient of variation, standard deviation
 
Self-reported measures: # of severe hypoglycemic events in prior 4 months: # of moderate hypoglycemia events in past 4 weeks; # of nocturnal hypoglycemic events in past 6 months; hypoglycemia unawareness; fear of hypoglycemia; diabetes knowledge; diabetes self-efficacy
 
Hemoglobin A1c
 
Hypoglycemia-related healthcare utilization: total number of urgent care, emergency department and inpatient visits for hypoglycemia as primary or principal diagnosis collected from the electronic health record (EHR)

Roles and Responsibilities

[name], MPH

Principal investigator and research physician

- Design and conduct of the study
- Preparation of protocol and revisions
- Overseeing and directing the study team and all implementation and data collection
- Leading Stakeholder Advisory Committee meetings
- Leading analyses and publication of study reports

Study Team:

Name, degree(s)	Role
[name], MS	Biostatistician
[name], MRCP (UK)	Consultant
[name], MS	Project Manager
[name], MA, MPH	Qualitative Research Associate
[name]	Patient partner and Co-Investigator
[name]	Family member partner and Co-Investigator
[name]	Qualitative Lead and Co-Investigator
[name]	Co-Investigator
[name]	Co-Investigator
[name], MS	Programmer Analyst
[name]	Implementation Lead and Co-Investigator
[name]	Endocrinologist
[name], BSc (Hons Biochem), [name], FRCP (Ed)	Consultant
[name]	Biostatistician and Co-Investigator
[name] CPsychol FFBPsS	Consultant
[name]	Family member partner and Co-Investigator
[name], MFA	Patient partner and Co-Investigator

Study team responsibilities:

- Agreement of final Study Protocol (*All*)
- Adaptation of MyHC-T2D; development and oversight of interventions (*EL, JN*)

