To determine if proactive care management plus MyHC-T2D is superior to proactive care management alone at preventing self-reported severe hypoglycemia in adults with type 2 diabetes at high risk for severe hypoglycemia. The primary outcome will be assessed through self-report via study survey at 14-months post baseline.

1b.2 Secondary objectives

1b.2.a Key secondary objectives

Key secondary outcomes will be assessed at 14-months post baseline through self-report in study survey (SR), continuous glucose monitors (CGMs; study participants will wear CGMs for 10 days), and electronic health records (EHRs).

1. To determine if proactive care management plus MyHC-T2D is superior to proactive care management alone in adults at high risk for severe hypoglycemia for the following:
 - Reducing percentage time with biochemical hypoglycemia (CGM assessed)
 - Reducing biochemical hypoglycemic events (CGM assessed)
 - Reducing the frequency of high blood sugars and reducing variability of blood glucose levels (CGM assessed)
 - Reducing number of severe hypoglycemic events in prior 4 months (SR assessed)
 - Reducing hypoglycemia unawareness (SR assessed)
 - Reducing number of self-reported moderate hypoglycemic events (SR assessed)

- Reducing fear of hypoglycemia (SR assessed)
- Reducing frequency of nocturnal hypoglycemia (SR assessed)
- Improving diabetes and hypoglycemia knowledge (SR assessed)
- Improving diabetes self-efficacy (SR assessed)
- Reducing hypoglycemia related healthcare utilization, including urgent care, Emergency Department and inpatient visits related to hypoglycemia (EHR assessed)

2. To assess differences in glycemic control, indicated by Hemoglobin A1c, between study participants in the proactive care management plus MyHC-T2D group and the proactive care management alone group.

1b.2.b Other secondary Objectives

Conduct a mixed methods process evaluation to evaluate the fidelity of implementation of intervention components, and clarify the causal pathway if intervention effects are found.

1c. Trial design

This study is an individually randomized controlled trial (RCT) comparing proactive care management^{30,31} to proactive care management plus MyHC-T2D.^{25,32}

2. Methods: Participants, interventions and outcomes

2a. Study setting

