2d.2 Secondary outcome measures

- Outcomes measured by Continuous Glucose Monitor, over 10 days, at baseline and 14-month assessment:
 - Percent time with biochemical hypoglycemia (<54 mg/dL);
 - Number of Level 2 biochemical hypoglycemic events (15 or more minutes <54 mg/dL).
 - Percent time biochemical hypoglycemia (< 70 mg/dL)
 - Number of level 1 hypoglycemic events (≥ 15 minutes at 54 - 69 mg/dL)
 - Number of nocturnal hypoglycemic events (≥ 15 minutes < 70 mg/dL between midnight and 6 am)
 - Percent time 70 to 180 mg/dL
 - Percent time above 180 mg/dL
 - Percent time above 250 mg/dL
 - Average blood glucoses, mg/dL
 - Standard deviation of glucose
 - Coefficient of variation for glucose (%CV)
 - Glucose management indicator
- Outcomes measured by self-report survey at baseline, 6, 10, and 14 months:
 - Number of severe hypoglycemic events in prior 4 months;
 - Hypoglycemia unawareness measured by the single item Gold survey;^{35,36}
 - Number of symptomatic⁴⁸ hypoglycemic events in the prior 4 weeks;⁴⁶
 - Fear of hypoglycemia using the Hypoglycemia Fear Survey-II;⁴⁹
 - Number of nocturnal hypoglycemia events (defined as “during sleep”) during past 6 months;⁵⁰
 - Diabetes and hypoglycemia knowledge with the revised Diabetes Knowledge Test;⁵¹
 - Diabetes self-efficacy using the 8-item Diabetes Self-Efficacy scale.⁵²

- Outcomes defined based on data collected from the EHR:
 - Hemoglobin A1c (HbA1c). The most recent HbA1c measures in the 12 months before baseline will be used for the baseline measure. Most recent measures within the past 3 months will be collected at 14 months. If the participant has not had an HbA1c within the past 3 months at 14 months, they will be asked to have one for the study.
 - Hypoglycemia-related healthcare utilization: total number urgent care, emergency department and inpatient visits for hypoglycemia as primary or principal diagnosis.

Figure 2 shows the relationship between outcome measures and study activities. Due to cost and participant burden, we will collect CGM measures only at baseline and at 14 months. We will measure all secondary outcomes including potential mediators of the intervention, at 6, 10 and 14 months after baseline assessment to identify potential early vs. later effects of the intervention.³²

Outcome Measures and Study Activities

Enrollment call,
Baseline Measures

[figure not shown]

Figure 2: Outcome measures and study activities

2e. Participant timeline

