Prior to conducting analysis of 14-month outcomes, we will look at the baseline distribution of the self-reported number of severe hypoglycemic events in the prior 12-months collected at baseline. If more than 60% of enrolled patients report 2 or more events, we will revise the primary outcome to be defined as the self-reported *number* of severe hypoglycemic events in the past 12-months, measured at 14-months post baseline (a count rather than a binary outcome and fit a Poisson regression model to estimate the rate ratio for severe hypoglycemia events for the MyHC-T2D group relative to the care management group. We will assess model fit, and consider zero-inflated models as an alternative, if the number of participants reporting zero events violates distributional assumptions of the Poisson model. If primary analyses use the binary outcome measure (i.e. fewer than 60% of patients report 2 or more events in the 12-months prior to baseline), but 40% or more of respondents report 2 or more events at 14-months, we will do a secondary analysis with the count variable as the outcome.

Generalized linear regression models estimated with GEE and robust sandwich errors will also be used to estimate intervention effects on secondary outcomes, with link function and error distribution appropriate for each outcome. For secondary outcomes measured at multiple follow-up time points (6-, 10- and 14-months post-baseline), we will fit a single regression model that includes outcome measures from all follow-up time points. Models will include indicator variables for time, intervention group, and interaction terms between these variables, to estimate intervention effects at each time point. Models will adjust for age, sex, risk score and the baseline measure of the outcome. For hypoglycemia-related health care utilization (urgent care and emergency department visits, hospital admits), we will follow a similar analytic plan as the primary outcome, including the process to determine whether to model these outcomes as binary or count variables.

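### The 4-month severe-event count is collected over all of months 2–14, but the plan estimates its effect only window by window, and no combined rate ratio is specified

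*Combined protocol and SAP*

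**What the plan says.** Section 2d.2 lists "Number of severe hypoglycemic events in prior 4 months" under "Outcomes measured by self-report survey at baseline, 6, 10, and 14 months". It gives the reason for repeated measurement: "to identify potential early vs. later effects of the intervention".

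Section 4c then says of secondary outcomes measured at several follow-ups that "we will fit a single regression model that includes outcome measures from all follow-up time points", and continues: "Models will include indicator variables for time, intervention group, and interaction terms between these variables, to estimate intervention effects at each time point". It names no average or cumulative effect.

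Two other places fix the reading time. Section 1b.2.a says "Key secondary outcomes will be assessed at 14-months post baseline", and the outcome table at the front says "All secondary outcomes assessed 14 months after baseline". The table adds that, in the intervention arm, this is about 12 months after the main part of the programme.

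**The concern.** For a scale such as the Gold score or the fear survey, the value at month 14 is a natural endpoint. A count with a 4-month recall is different. At months 6, 10 and 14 it covers months 2–6, 6–10 and 10–14. The windows do not overlap, and together they cover the same 12 months as the primary outcome. Reading the count at month 14 sets aside the events of months 2–10, which is about two thirds of them if the rate is constant. The objective in section 1b.2.a is simply to reduce the number of severe events.

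The primary outcome covers months 2–14 as yes/no, so it cannot show a fall from several events to one. A 12-month count is analysed only if a trigger is met: it becomes primary if more than 60% report two or more events at baseline, or it is a secondary analysis if 40% or more do so at month 14. If neither is met, the 4-month item is the only planned analysis of how often participants report severe events.

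**Working it through.** **Inputs from the documents.** Section 2f: 102 analysed per arm (80% response), 60% control risk over 12 months, type I error 0.05. Sections 2d.2 and 4c: 4-month recall at months 6, 10 and 14, with one effect per time point. No event rate, dispersion or within-person correlation is given for the count.

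**Assumptions.** Two-sided test, constant event rate, common rate ratio in all windows, 102 per arm at every survey, no baseline adjustment, no clustering by training cohort.

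**Step 1: the plan's own power.** Two proportions, pooled variance, no continuity correction: z = [d√n − 1.96√(2p̄q̄)] / √(p₁q₁ + p₂q₂).
- 60% v 37.4%: (0.226 × 10.10 − 1.96 × 0.707) / 0.689 = 1.30, so power is 90.4% (stated 90%).
- 60% v 40.3%: (0.197 × 10.10 − 1.96 × 0.707) / 0.693 = 0.87, so power is 80.8% (stated 80%).

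Both figures reproduce. No power is stated for the 4-month count.

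**Step 2: one window against all three, persistent patient differences only.** Let μ be the control rate per year, k the between-patient dispersion, R the rate ratio, and T = 1 (12 months) or 1/3 (one window). Then

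Var(log R) = [1/(μT) + k + 1/(RμT) + k] / 102.

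Under these assumptions the equally weighted average of the three window-specific log ratios has the same variance as T = 1. The rate μ is set so that 60% of controls have an event in 12 months: μ = −ln 0.4 for k = 0, otherwise (0.4^(−k) − 1)/k.

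For R = 0.6 (log 0.6 = −0.511) and k = 0, μ = 0.916:
- 12 months: SE = √[(1/0.916 + 1/0.550)/102] = 0.169; 0.511/0.169 = 3.02; power = Φ(3.02 − 1.96) = 86%.
- One window: SE = 0.169 × √3 = 0.293; 0.511/0.293 = 1.75; power = Φ(1.75 − 1.96) = 42%.

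| k | μ | SE, 12 months | SE, one window | Power, 12 months | Power, one window |
|---|---|---|---|---|---|
| 0 | 0.916 | 0.169 | 0.293 | 86% | 42% |
| 1 | 1.500 | 0.193 | 0.268 | 76% | 48% |
| 2 | 2.625 | 0.222 | 0.263 | 63% | 49% |
| 3 | 4.875 | 0.253 | 0.274 | 52% | 46% |
| 4 | 9.516 | 0.285 | 0.294 | 43% | 41% |

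At R = 0.563, the Poisson equivalent of 60% v 40.3% (ln 0.597 / ln 0.4), one window against 12 months gives 49% v 92% (k = 0), 56% v 84% (k = 1), 58% v 73% (k = 2), 55% v 62% (k = 3) and 50% v 52% (k = 4).

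**Step 3: simulation with variation between windows as well.** Counts were gamma-Poisson, with person variance 0.5–2 and window variance 0.5–1, calibrated to the same 60%. There were 4,000 trials per setting and robust standard errors. At R = 0.6, power was 35–42% at month 14 and 54–79% for the average. With no overdispersion it was about 42% and 87%, and with very persistent patient differences 43% and 45%. Repeat runs agreed to within about two points.

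**Step 4: why the range is wide.** With equal within-person correlation r, the average has (1 + 2r)/3 of one window's variance. One window's SE is then 1.73 times that of the average at r = 0, 1.53 times at r = 0.14, 1.26 times at r = 0.44, and nearly equal when r is about 0.9.

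**The case against.** The time-specific estimates are deliberate. Section 2d.2 wants early and later effects separated, and reading at month 14 asks about a sustained effect. The first window also overlaps the end of delivery: the programme runs about three months and the booster call comes about three months after the intervention starts. An equal-weight average therefore answers a different question. This stands, and it is a reason to add the average and not to replace the month-14 reading.

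Severe events over months 2–14 are already tested by the primary outcome, and as a count when multiple events are common. This also stands, but the count depends on the triggers and the primary is yes/no.

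A reader might infer that the plan inflates its type I error. In simulation, at least one of three unadjusted window tests is significant in about 12–18% of null trials. The plan contains no such rule. It names one time, month 14, so the figure only warns against choosing a window afterwards.

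A reader might also infer that people who miss month 14 are lost. All follow-ups enter one model, and with attrition above 10% section 4c considers imputation or weighting, which could use the earlier reports. They contribute directly only to an averaged effect, but they are not excluded by design.

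Finally, recruitment is complete and the biostatisticians can see unblinded data for monitoring reports (section 3b). A late change of the headline would invite criticism as post hoc. That affects how and when the addition is recorded.

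**Conclusion.** The gap is real: the data for a 12-month rate ratio are collected and modelled, but none is specified, and the stated month-14 comparison uses one window of three. Under a common rate ratio the averaged contrast had more power than a single window in every scenario run. At a rate ratio of 0.6, the gain is 45 points or so with no overdispersion and roughly 14 to 40 points with moderate overdispersion. It is only 2 to 3 points if patient differences are very persistent.

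The documents do not support saying that much power is lost whatever the data look like, because the dispersion is unknown. Adjustment for the baseline count should reduce persistent dispersion and move towards the larger losses, by an amount that cannot be stated. Clustering by training cohort was left out; it would lower both power figures, and a cohort effect that persists over time would not average out. Nor is the month-14 reading an error. This is a secondary outcome with no claimed power, and the primary conclusion is unaffected. The addition is worth making because it is cheap and the conditional 12-month count does not reliably cover the same ground.

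**What to change.** In section 4c, add for this count one pre-specified rate ratio averaged with equal weight, on the log scale, over the month 6, 10 and 14 windows. Take it as a contrast of the group and group-by-time terms in the GEE model already planned. Include everyone with at least one follow-up report, and name it as the overall estimate of effect on severe-event frequency. Keep the month-14 ratio and the other time-specific ratios, reported for early versus later effects. Add a matching line to section 1b.2.a and the outcome table so that the role of each estimate is clear.

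Date and document the addition before outcome comparisons by arm are examined, through the amendment route in section 5b if it counts as a change of objectives or design.

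The cost is a few sentences and one contrast, with no new data. The downside is that an effect which changes over time is blended in the average, and the first window includes the end of delivery. The time-specific ratios still show both.

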We estimate 256 patients (128 randomized to proactive care management, and 128 randomized to MyHC-T2D) will consent and complete the baseline survey. To account for loss to follow-up, we assume an 80% response rate for the primary outcome measured at 14-months, for an analytic sample size of 204 (102 per group). Power calculations for comparing two independent proportions and assumed a 0.05 type I error rate. Assuming 60% of patients in the proactive care management group will self-report having had a severe hypoglycemia event in 12-month look back (yes/no), we have 90% power to detect a 22.6% absolute difference between groups (i.e. 37.4% severe hypoglycemia rate in MyHC-T2D arm) for the primary outcome. We have 80% power to detect an absolute difference of 19.7% between groups. Our study has power to detect a meaningful difference (30% or more reduction in frequency of self-reported severe hypoglycemia events).⁵⁴ Other studies including for the original *my hypo compass* have similar or larger effects on severe hypoglycemia reductions.²⁵⁻²⁹ We also have 80% power to detect a 1.4% difference and 90% power to detect a 1.6% difference between groups in the secondary outcome of the percent time with biochemical hypoglycemia (<54 mg/dL); this difference is consistent with the effect seen with the original *my hypo compass*.^{25,32}

2g. Recruitment

We will recruit the study population in two steps.

Step 1, Automated risk stratification: We will identify a cohort of adults (≥ 18 years) with T2D receiving primary care at KPWA. We will identify all individuals with either a current prescription for insulin or who have intermediate-to-high risk for a SH event based on our hypoglycemia risk-stratification tool.

Step 2, Phone screening for verbal consent and to identify patients at highest SH risk: We will mail eligible participants an invitation with study brochure and notification that staff will call them about the study. KPHRI Survey Research Program (SRP) members will then call the potential participant to explain the study, assess eligibility and interest, and conduct informed verbal consent with those who are eligible and interested. We expect 1001 eligible. Based on a similar recruitment⁵⁵ and participation in other diabetes education trials, we anticipate at least 25% will consent and complete baseline data collection.⁵⁶

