Standards for Preventing and Handling Missing Data. Outreach with repeated calls will maximize response rates of follow-up phone surveys. Response rates and data collection will be monitored and if attrition is greater than 10%, statistical methods will account for potential selection bias. We will compare baseline characteristics of responders and non-responders and consider multiple imputation or inverse probability weighting (IPW) to account for potential bias due to missing data.

Addressing HTE standards.

Exploratory analyses will assess whether treatment effects vary by patient characteristics including age (under 75 years vs. 75 years and older), sex, race/ethnicity, comorbidities, insulin use and/or sulfonylurea use, baseline IAH presence, and baseline SH history. We will include interaction terms between randomization group and these characteristics in the primary and secondary outcome models to estimate comparative effectiveness by subgroup.

We provide a brief description of the power we estimate we will have for some subgroup analyses. For those with minority racial and ethnic backgrounds (approximately 30% of participants), we will have 90% power to detect a 39% difference and 80% power to detect a 35% difference in the rate of severe hypoglycemia between comparators for this subgroup. For females (approximately 50% of participants) and those the 65 years of age or older (approximately 50% of participants), we will have 90% power to detect a 31% difference in the rate of severe hypoglycemia and 80% power to detect 27% difference. All of these effect sizes are smaller than those in the MyHC-T2D study in patients with type 1 diabetes.³⁴

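### The exploratory age interaction uses only the cut at 75, which loses roughly 40-55% of the information on a trend in effect with age under stated assumptions; test age in years and keep the cut for display

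*Combined protocol and SAP*

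**What the plan says.** Section 4c, under the heading on HTE standards, describes exploratory analyses of whether "treatment effects vary by patient characteristics including age (under 75 years vs. 75 years and older), sex, race/ethnicity" and several other baseline factors modify the effect. The method is "We will include interaction terms between randomization group and these characteristics in the primary and secondary outcome models", with the aim of giving effect estimates by subgroup. No continuous or spline interaction with age appears anywhere.

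Other parts of the document bear on this:

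- Section 3a stratifies randomization by age, 18-74 versus 75+. The analysis cut is therefore a design factor fixed in advance.
- Section 4c lists age as an adjustment covariate in the outcome models without giving its functional form.
- The subgroup power text in section 4c uses a different age cut, "those the 65 years of age or older (approximately 50% of participants".
- Awareness is listed as a modifier by presence or absence of impairment. Section 2d.2 collects it as "Hypoglycemia unawareness measured by the single item Gold survey".

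**The concern.** Cutting a continuous modifier in two treats everyone on the same side as alike. With entry from age 18, participants aged 30 and 74 fall in one group, while those aged 74 and 75 fall in different groups. If benefit rises or falls gradually with age, the two-group contrast uses only part of the evidence, and the loss grows as the split becomes more uneven. Interaction tests in a trial of about 204 analysed participants are weak to begin with. The cost is a lower chance of seeing a real age trend that the data on hand could show.

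**Working it through.** **Inputs from the documents.** Analysed sample 204, 102 per arm, control risk 60%, alpha 0.05 (section 2f; two-sided assumed, as sidedness is not stated). Allocation 1:1 (section 3a). About 50% aged 65 or older (section 4c), hence a median of about 65.

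**Assumptions.** Ages roughly normal with SD 10 to 15 years. The log relative risk changes linearly with age. The documents give neither the age SD nor the share aged 75+.

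**The plan's own power figures.** Section 2f states: "Power calculations for comparing two independent proportions and assumed a 0.05 type I error rate". With p̄ the mean of the two risks and d their difference,

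power = Φ{[d√n − 1.96√(2p̄(1−p̄))] / √(p₁(1−p₁) + p₂(1−p₂))}.

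- 0.60 vs 0.374, n = 102: (2.283 − 1.385)/0.689 = 1.30, power 90.4%. The plan says "we have 90% power to detect a 22.6% absolute difference between groups".
- 0.60 vs 0.403, n = 102: power 80.8%. The plan says 80% for 19.7 points.
- Half the sample, n = 51 per arm (the subgroup aged 65+): 89.5% at 31 points and 78.9% at 27 points, against the stated 90% and 80%.

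The figures reproduce. They cover the overall effect and the effect within a subgroup. None concerns an interaction, and none uses the cut at 75.

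**Information kept by the cut.** For a normal modifier and a linear interaction, the share kept relative to a linear term is φ(c)²/[q(1−q)], where c = (75 − 65)/SD and q = 1 − Φ(c) is the share aged 75+. The standard error ratio is 1/√(share kept).

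| SD | c | q | φ(c)² / q(1−q) | kept | lost | SE ratio | 204 act like |
|---|---|---|---|---|---|---|---|
| 10 | 1.000 | 0.159 | 0.05855/0.13348 | 44% | 56% | 1.51 | 89 |
| 12 | 0.833 | 0.202 | 0.07947/0.16139 | 49% | 51% | 1.43 | 100 |
| 15 | 0.667 | 0.252 | 0.10205/0.18874 | 54% | 46% | 1.36 | 110 |

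At SD 12, a trend with 80% power on the continuous scale has Φ(√0.492 × 2.80 − 1.96), about 50%, with the cut.

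**Sensitivity.** If the share aged 75+ is 10%, the loss is 66%; at 50% it is 36%. Non-normal age shapes with median near 65 gave losses of 44% to 71%.

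**Simulation of a modified Poisson model with robust SE** (204 participants, control risk 60%, relative risk 0.70 at age 65, log relative risk slope 0.35 per SD of age, 1,500 runs, no session clustering):

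| SD | power, age in years | power, cut at 75 | information lost |
|---|---|---|---|
| 10 | 74% | 52% | 48% |
| 12 | 75% | 54% | 43% |
| 15 | 71% | 52% | 40% |

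**Other slopes** (same sample size, 20% aged 75+, 2,500 runs; continuous vs cut): 12% vs 8% at 0.10 per SD, 20% vs 13% at 0.15, 45% vs 28% at 0.25, 85% vs 64% at 0.40. With no interaction the rejection rates were 5.6% vs 3.9%, so a small part of each gap reflects test size.

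**True step at 75** (SD 12): the cut had 91% power and the linear term 64%. With a smaller step of 0.5 in log relative risk, the figures were 38% and 22%.

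**The case against.** The analysis is labelled exploratory and is aimed at estimates by subgroup. The cut is a stratification factor chosen in advance, so it is not arbitrary. If the effect changes in a step at 75, the cut is the better test. At modest slopes both forms have low power, and the slope where the continuous test exceeds 80% (0.40 per SD) is extreme: the relative risk would run from 0.70 × e^(−0.4) = 0.47 one SD below the mean to 0.70 × e^(0.4) = 1.04 one SD above it. All of this stands. It supports reporting by the 75 stratum and keeps the point minor. It does not support making the cut the only interaction test, because the documents give no reason to expect a step at exactly 75.

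A reader might infer two stronger claims.

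- **That half the information is lost outright.** The documents do not show this. The figure depends on an unstated age SD, on distribution shape and on linearity. The 50% aged 65+ is a planning approximation that may predate the widening of entry to age 18 in protocol version 04.
- **That the same loss applies to awareness.** The documents give no range, cut or distribution for the Gold item, so no loss can be computed. Impaired awareness is also part of an entry criterion (section 2b), which makes presence or absence a natural subgroup.

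**Conclusion.** The point holds for age, as a low-cost improvement to an exploratory analysis. As the sole interaction test, the cut at 75 loses roughly 40-55% of the information on an age trend. This rests on a median age of about 65, roughly normal ages with SD 10 to 15, and near-linear modification. The range combines the formula (46-56%) with the simulation (40-48%); other age shapes could give more. The gain from a continuous term is real but will not make the trial well powered for modest effect modification. The primary estimate, its test and the sample size are untouched.

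**What to change.** In the HTE paragraph of section 4c, state that:

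- the arm-by-age interaction is tested with age in years as a continuous term, and the age main effect in that model takes the same form;
- a simple non-linearity check accompanies it, such as a spline with few knots;
- the cut at 75 is kept to report stratum-specific estimates with confidence intervals, as display only. This settles in advance which result counts as the interaction test if the two disagree.

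An interaction with the Gold score can be added as an optional sensitivity analysis, with no gain claimed.

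The cost is a short text change, one interaction term and one check per outcome model, on data already collected. Recruitment is complete, so the change should be dated and made before effect modification is examined by arm. The downside is lower sensitivity of the linear term to a true step at 75, which the retained display and the non-linearity check partly cover.
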